We will continue to consecutively enroll participants on post-operative day 2 from the adult female patient population receiving c-section surgery at KDH during a 14-month period. Randomization into the three study arms will take place at time of discharge. We will enroll 1092 participants in this phase of the study, 364 per study arm. Once enrolled, there will be no special retention strategies so as not to interfere with the outcomes under investigation in Aim 4 (return to care) or Aim 5 (process measures describing the CHW-mHealth intervention implementation). If the patient is still in the hospital 10 days following surgery, they will be excluded from the study given the inability to be randomized properly to the three arms of this phase. We will include patients from Mahama Refugee Camp when collecting information about the hospitalization and outcomes. However, these patients will not be asked to return for follow-up.

Sealed study packets, prepared in advance, will be available at KDH. Each study packet will have the arm assignment for the patient, which will be randomly assigned during the preparation of the materials using a random number generator. Both the research staff and the patient will be unaware of the arm assignment during the consent process and the assignment will be revealed only after the patient has agreed to participate. In this phase, no participants will receive travel vouchers, to ensure appropriate comparison between the intervention and standard of care groups. Per standard of care, all patients will receive information on the signs of SSI and will be instructed to return as soon as any of these present. (Appendix A).

STUDY PROCEDURES:

This research includes two distinct phases. During the first phase, we will optimize the SSI screening protocol by piloting it among a cross-section of patients receiving surgery at KDH, Rwanda. In the second phase, we will randomize patients receiving surgery at KDH to one of three arms – standard of care and the two intervention arms. At the conclusion of the study, we will compare rates of return and severity of SSI at return among the three arms and report process indicators describing the implementation of the CHW-mHealth interventions in the two intervention arms. In this study, patients will be assessed at 10 days after their operation, as symptoms for SSI usually develop during the first 6-9 post-operative days.²³

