All consenting participants will have basic demographic and socioeconomic data collected by self-report via a survey administered by the study data collector at time of discharge. The study data collector will extract additional clinical data from the patient file. At time of discharge, participants will receive surgery follow-up instructions (Appendix A), including a set of warning signs for SSI and when to return to a health center, per standard of care. Additional human subjects contact will depend on study arm assignment. Individuals in Arm 1 will be visited at home by the sCHW who will administer the optimized SSI protocol via the mHealth device. Following the screening, the sCHWs will use the cell phone to photograph the surgical wound and record the GPS location of the visit. Individuals in Arm 2 will be phoned by the sCHW who will administer the SSI protocol over the phone. Individuals in Arm 3 will not have any additional contact beyond standard of care (Figure 1).

Figure 1:

BIOSTATISTICAL AND QUALITATIVE ANALYSIS:

Phase 1:

At the time of enrollment, study staff will administer a basic survey to record self-reported data on patient demographics (gender, age, weight, height, education level, location of residence, distance to hospital) and socioeconomic status (monthly household income, land ownership, cost of transport as a barrier to receiving health care). Study staff will also extract data from clinical charts on past medical history, type of surgery, time from surgery recommendation to operation, pre-operative antibiotic use/time, wound class, and any documented surgical complications. Clinical information will continue to be collected up to 90 days for any patients who are never discharged or for any patient who is readmitted for a surgical complication. For patients that are transferred to Kigali for tertiary care, we will use data collected routinely collected by the Right to Health Care program to complete their follow up information.

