Specific Aim 1: During the follow-up screening visit, patients will be evaluated in two different steps. First, the patient will be screened by a CHW who will use the mHealth tool to administer the basic screening questions. The mHealth application will prompt the CHW to evaluate for warmth, increased pain, increased swelling, increased firmness of the wound, wound opening, and fluid drainage and quality. The CHW will take photo of the wound on the mHealth tool. Second, a GP will perform a clinical assessment and provide responses to two basic questions: 1) Do you diagnose the patient as having an SSI? And 2) Do you identify any other post-operative

complications that would warrant the patient's return to the clinic for physician review? These data will be considered the gold standard against which to compare the SSI screening protocol. The GP will also comment on the 6 characteristics from the mHealth tool for comparison.

Specific Aim 2: For one month of Phase 1, study nurses will observe the clinical interactions with patients during rounding and document in a case observation form (Appendix B) the prescription and taking of antibiotics during admission and at discharge.

Specific Aim 3: To assess the WASH infrastructure at the hospital, data collectors will administer a hospital assessment form (Appendix C). To assess variability, the data collectors will administer an abbreviated version of this form every 4 hours over the course of one week. At the follow-up visits, mothers will be asked about the access to sanitation facilities at home.

Analysis and Outcomes:

Aim 1:

Patients who are still admitted at the follow-up will be excluded from the developing of the screening algorithm. At 4 months into Phase 1, we will assess the validity of the SSI screening protocol. In this first assessment we will identify a cutoff (c) by optimizing the area under the receiver operating characteristic curve. We will consider the screen positive if the patient meets at least c of the 6 criteria. If the sensitivity of SSI screening protocol is less than 90% or the specificity is less than 80%, we will modify and optimize the screening protocol. Steps for modifying the algorithm include the following:

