Basic demographic and clinical data will be recorded at baseline by study staff, as described in phase 1. For Arms 1 and 2, addresses/phone numbers and availability will be documented for patient follow-up. At ten post-operative days (± 3 days), sCHWs will visit patients in Arm 1 at the address provided. The sCHW will be assisted by a local village CHW to identify the patients' homes. Once there, the sCHW will administer the SSI screening protocol with prompting from the phone, record responses into the phone, take a photo of the wound, and take GPS coordinates. Patients in Arm 2 will be phoned by the sCHW on the tenth post-operative day (± 3 days). The sCHW will administer the SSI screening protocol over the phone, prompted by the smartphone application to ask the appropriate questions. For both arms, patients identified as having an SSI will be referred back to KDH for care. These patients will also be asked a set of questions to assess for possible barriers to return of follow up. In this phase, patients will not receive financial support to return to the clinic. Patients not identified with SSI will be reminded of the warning signs and follow-up instructions. Patients still hospitalized at the hospitalized on their assigned screening day will be excluded from the study as they will not be eligible for the expected study follow up.

A patient tracker log at the hospital will be used to document patient return for follow-up care. The log will also document patients that self-present with potential SSI. Study staff will extract from the clinical chart the presence of an SSI, severity, treatment obtained, need for operative intervention, hospitalization, and/ or complications as recorded by a KDH GP. During the study period, clinical charts will be audited for completeness and GPs will be trained in data quality to ensure the accuracy of this clinical data. In addition, study staff will track process measures related to Arms 1 and 2.

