Patients in Arms 1 and 2, who are determined by the sCHW to have a suspected SSI and referred back to care, but fail to return back to care within one week will be identified. Data collectors will return to these patients' homes at 22-30 days post-operation to interview them on why they failed to return to care. The interviews will be semi-structured, including questions on established barriers to care and allowing for open-ended response. A random sample of patients in Arm 3 will be visited at home at 22-30 days post-operation by data collectors who will

interview them on their follow-up care procedures. The interviews will be semi-structured, including questions on standard care paths and allowing for open-ended response.

For a subset of 50 patients, we will administer at discharge a Financial Risk Protection Survey (Appendix D), an existing validated tool, to understand the total costs of care and the costs relative to normal household expenditures.

Analysis and Outcomes:

Aim 4:

For Aim 4, we will compare the proportion of patients who return for follow-up with an SSI in Arms 1 and 2 to Arm 3 (standard of care) using a two-sided, two-sample test of proportions at the $\alpha=0.05$ significance level. We will use a logistic regression model to assess the impact of study arm on measures of severity at presentation (for example, readmission to hospital), controlling for potential confounders collected at enrollment. All analyses will be completed as intention to treat, regardless of whether the patient had contact with the sCHW or was screened by the mHealth tool in Arms 1 and 2. For Aim 4, for Arms 1 and 2, we will report percent for each of the process measures (for example, percent of home visits or calls completed on time) with 95% confidence intervals. We will assess the impact of study arm on measures of severity at presentation, controlling for potential confounders collected at enrollment. We will describe standard of care patient follow-up behavior using results from Arm 3. We will also report surgery-related reasons for return to care beyond SSI. We will perform a sensitivity analysis to determine under what range of SSI rates the results are still valid.

Aim 5:

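### The Phase 2 SSI endpoint is a routine chart diagnosis with no stated criteria or masking to referral, while sCHW referrals for suspected SSI arise only in Arms 1 and 2

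*Combined protocol and SAP*

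**What the plan says.** The Aim 4 analysis (Analysis and Outcomes, Phase 2) states that "we will compare the proportion of patients who return for follow-up with an SSI in Arms 1 and 2 to Arm 3", and the Power Analysis says Aim 4 drove the Phase 2 sample size.

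The source of the endpoint is in the Phase 2 part of Biostatistical and Qualitative Analysis: "Study staff will extract from the clinical chart the presence of an SSI, severity, treatment obtained". The same sentence ends with "hospitalization, and/ or complications as recorded by a KDH GP". Charts are to be audited for completeness, and GPs trained in data quality so that the data are accurate. No SSI case definition, masked assessor or adjudication is described for Phase 2.

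The route to the GP differs by arm. Of Arms 1 and 2 the plan says "For both arms, patients identified as having an SSI will be referred back to KDH for care". Of the control arm, Study Procedures, Phase 2, says "Individuals in Arm 3 will not have any additional contact beyond standard of care". Concealment covers consent only: "the assignment will be revealed only after the patient has agreed to participate".

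Phase 1 is more structured. Under Specific Aim 1 the GP answers a set question, "Do you diagnose the patient as having an SSI", and comments on the six wound signs. Item 3 of the data list under Monitoring and Quality Assurance puts these answers on a study paper form. The screen is to be modified "If the sensitivity of SSI screening protocol is less than 90% or the specificity is less than 80" percent.

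**The concern.** Charting an SSI involves judgement, above all for a borderline wound. In Arms 1 and 2 the intervention sends extra women to the person making that judgement, and they come because a screen suggested infection. Some will be uninfected. Each one charted as SSI adds an event to an intervention arm, and no matching stream of referrals exists in Arm 3.

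This does not depend on the GP knowing about the referral. A GP who knew nothing of it, but was less than perfectly specific, would still chart more false SSIs where more uninfected women are examined. Knowledge of the referral would add to this.

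At stake is what a higher rate of return with SSI means: more infected women reaching care, or partly more labelling. Risks and Discomforts accepts that an sCHW may reach a wrong diagnosis, but treats it only as a risk to the patient. The planned sensitivity analysis over SSI rates and the intention-to-treat rule do not deal with misclassification that differs by arm.

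**Working it through.** **Inputs from the plan**
- 364 women per arm, 15% SSI rate, 55 SSI cases per arm, 6% v 12% returning with SSI (22 v 44), two-sided 0.05, stated power 81% (Power Analysis).
- 80% specificity and 90% sensitivity: the limits that trigger modification of the screen (Analysis and Outcomes, Aim 1).

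**Assumptions, not in the plan**
- Phase 2 specificity of 80% or 90%.
- Share of wrongly referred women who return: 40% or 80%, borrowed from the plan's return rates for SSI cases.
- Share of those returners charted as SSI: 10% to 25%.
- Every woman in the arm is screened.

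**Step 1: reproduce the stated power.** One intervention arm v Arm 3, uncorrected z-test:
- Standard error under the null: √(2 × 0.09 × 0.91 / 364) = 0.0212.
- Standard error under the alternative: √((0.12 × 0.88 + 0.06 × 0.94) / 364) = 0.0211.
- z = (0.06 − 1.96 × 0.0212) / 0.0211 = 0.87, so power is 80.9%. This matches the stated 81%.

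**Step 2: wrong referrals per arm.** Women without SSI: 364 − 55 = 309. At 80% specificity, 309 × 0.20 = 62 are referred in error. At 90% specificity, 31 are.

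**Step 3: false events and their effect.** Excess proportion = 0.85 × (1 − specificity) × return share × charted share. The last column is the chance of a two-sided significant result when both arms have 22/364 true returns with SSI, by exact enumeration of the same z-test. With no excess it is 5.0%.

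| Specificity | Return | Charted as SSI | False events per arm | Excess (points) | Chance of significance |
|---|---|---|---|---|---|
| 80% | 40% | 10% | 2.5 | 0.7 | 6.6% |
| 80% | 40% | 25% | 6.2 | 1.7 | 14.8% |
| 90% | 40% | 10% | 1.2 | 0.3 | 5.4% |
| 90% | 40% | 25% | 3.1 | 0.85 | 7.5% |
| 80% | 80% | 10% | 5.0 | 1.4 | 11% |
| 80% | 80% | 25% | 12.4 | 3.4 | about 40% |

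For scale, the planned difference is 6 points, or 22 events.

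**Step 4: which rows fit a null effect.** If 80% of referred women return, then at 90% sensitivity 55 × 0.90 × 0.80 = 40 infected women return on referral. That is well above 22, so there is a real effect. At 40% return the figure is 55 × 0.90 × 0.40 = 20, close to 22. The 40% rows are therefore the coherent ones for a no-effect scenario.

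**Step 5: how many false events matter.** Against 22 events in Arm 3, 36 gives z = 1.92 and 37 gives z = 2.04. So 15 false events would produce significance with no extra infected woman returning. That is 15/62 = 24% of all wrong referrals at 80% specificity, counting those who do not return.

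**The case against.** The strongest reply is that the plan nowhere says what the GP is told. It describes referral to the hospital and a tracker log there, but no referral slip and no GP access to the log. A reader might infer that the GP knows the arm. The documents support only that masking is not stated. This stands, and the point is worded accordingly.

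A reader might also infer that the error can run only towards Arms 1 and 2. It need not. Over-diagnosis of women who present on their own can occur in any arm, Arm 3 included. A wrong negative screen, or a woman waiting for an expected visit, could lower the count in Arms 1 and 2; Risks and Discomforts names both a wrong sCHW diagnosis and delayed return. What remains specific to Arms 1 and 2 is the false-positive sCHW referral.

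The 40% figure is tempting as a headline. It needs uninfected women to respond to referral at 80% while infected women respond not at all, so it fits poorly with no true effect. It also assumes complete screening. If only 63% of Arm 2 were reached by phone (an assumption borrowed from the national phone-ownership figure in the Background), the excess falls from 3.4 to 2.1 points and the chance to about 20%. The 80% specificity is a trigger for change, not expected performance. Equally, it is no floor: the month-7 algorithm is adopted with no required minimum, and Phase 1 tests the screen in person, not by phone.

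Two further replies have some force. The Phase 1 question states no SSI criteria either, so the form alone is not enough. And the six signs are the initial screening items, so an endpoint built mechanically on them would partly repeat the screen that generated the referral. The fix allows for both.

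The GP training is meant to secure accuracy, not only completeness, but it neither fixes criteria nor hides the referral. Nor is the trial wholly unable to separate labelling from benefit: severity, treatment, presentation on referral and Arm 1 photographs allow partial checks.

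**Conclusion.** The concern holds in a limited form. The endpoint that sized Phase 2 is a routine chart diagnosis without stated criteria or stated masking, and only two of the three arms generate referrals for suspected SSI. Inflation in favour of Arms 1 and 2 is likely, but neither its net direction nor its size is established by the documents.

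On the scenarios that fit a null effect, the chance of a significant result per contrast is about 7% to 15% at 80% specificity and 5% to 8% at 90%, against a nominal 5%. The case with 80% specificity and 80% return, 11% to 40%, is an outer bound and not a forecast. All of these rest on assumed specificity, return and charting shares. The plan should be changed because the remedy is cheap and because structured findings cannot be recovered once return visits have been charted without them.

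**What to change.** In the Phase 2 data-collection text of Biostatistical and Qualitative Analysis:

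1. Have the KDH GP complete the Phase 1 assessment form (SSI yes/no plus the wound signs) at every return visit in all three arms.
2. Keep arm and referral source off that form and in the tracker log only.
3. Derive the Aim 4 SSI endpoint from the form by SSI criteria written before Phase 2 starts. These should not merely repeat the sCHW screening cutoff.
4. Report the charted diagnosis as a supporting analysis, and report SSI among returners separately for referred and self-presenting women.

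The cost is one short form per return visit, using an instrument that already exists. Sample size, referral and care are unchanged. Masking will be only partial, because a woman may tell the GP that she was referred, and a later masked reading of the forms could not undo that.

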Specific Aim 8: We will assess the direct and indirect costs incurred by the mother and her family, stratified by whether or not she has a surgical site infection, and describe the burden of these costs relative to the overall financial expenditures of the household.

SUBJECT SELECTION AND ENROLLMENT:

This study will follow patients who received cesarean-section surgery at KDH and reside in Kirehe District. KDH is a 145-bed facility operated by the Rwanda Ministry of Health (RMOH) and supported since 2005 by the medical non-profit organization Partners In Health (PIH). The hospital serves a catchment area of 364,000 people, primarily residing in rural, outlying villages. In preliminary work, we conducted a chart review that showed that 7.3% of obstetric surgical patients and 3.1% of non-obstetric surgical patients returned to the hospital with an SSI. Based on regional literature, we expect the true rate of SSI in patients receiving surgery KDH to be 10-20%.²²

Phase 1

Participants will be adult (≥ 18 years) patients receiving cesarean-section surgery at KDH over a seven-month enrollment window. All patients receiving a cesarean section (c-section) surgery at KDH who reside in Kirehe district will be eligible and will be invited to participate on post-operative day 2. We anticipate enrolling 525 post-operative c-section patients who received surgery at KDH during the seven-month period. Patients will be enrolled consecutively. We will include patients from Mahama Refugee Camp when collecting information about the hospitalization and outcomes. However, these patients will not be asked to return for follow-up.

Phase 2

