For consenting participants that are discharged prior to their 10-day post-operative screening, a study data collector will administer a simple self-report survey to collect basic patient demographic and socioeconomic characteristics on the day of discharge. They will be asked to return to the clinic for screening. In line with national policies, these participants will receive a voucher worth approximately US \$10, to compensate for travel and time, to return to the clinic. The voucher will be redeemed when the patient arrives to their assigned screening day. If a participant misses his assigned screening day, the participant will be contacted via his local community health worker.

Consenting patients that are not discharged prior to their 10-day post-operative screening will have demographic and socioeconomic data collected via self-report survey administered by the

study data collector as well as GPs and sCHW conducting the physical examination on the assigned screening day. These participants will not receive any voucher. Study staff will also extract clinical data from the patient files of all consenting participants.

[figure not shown]
We anticipate enrolling a minimum of 525 post-operative patients during the five-month period. With an estimated overall SSI rate of 15% based on existing literature and 10% loss-to-follow-up (LTFU), we expect 71 patients will have a GP-diagnosed SSI and 402 patients will not have a GP-diagnosed SSI.

PHASE 2:

After the screening protocol has been optimized in phase 1, new patients receiving c-section surgery at KDH will be enrolled and randomized to one of three study arms. Rates of return and severity of SSI at return across the three arms will be compared (Aim 4). We will also report process indicators to describe the implementation of the CHW-mHealth interventions (Aim 5). For patients that have contact with a sCHW (Arms 1 and 2), and are suspected to have a SSI and referred back to care but fail to return, we will assess their barriers to care (Aim 6). For patients that have no special follow-up, we will assess their post-operative follow-up practices (Aim 7). Embedded in this study will be a small sub-study on the costs of care and impact of these costs on family expenses (Aim 8).

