For Aim 5, we will report percent for each of the process measures with 95% confidence intervals. Process measures include: ability to find the patient's home (Arm 1), willingness to allow sCHW into home (Arm 1), percent of home visits completed (Arm 1), successful use of GPS (Arm 1), availability of phone (Arm 2), availability of patient when called (Arm 2), visits or calls completed on-time (Arms 1 and 2), percent of reports successfully transmitted via the application (Arms 1 and 2) and presentation to care upon referral (Arms 1 and 2).

Aim 6:

For Aim 6, we will identify potential predictors for failure to return, comparing those who were recommended in Arms 1 and 2 to return and did return to those who failed to return using logistic regression. Demographic and clinical predictors collected at enrollment will be used as potential predictors. All factors significant at the $\alpha=0.2$ significance level in the bivariate analysis will be considered for the multivariate analysis. We will build the final predictive model using backward stepwise regression, stopping when all factors remain significant at the $\alpha=0.05$. For those that fail to return to care, we will report their barriers to care using proportions and 95% confidence intervals. Responses to open ended questions will be transcribed and translated, and we will identify any unaddressed themes using a general inductive approach.

Aim 7:

For Aim 7, we will evaluate patient post-operative care behaviors using proportions and 95% confidence intervals. Responses to open ended questions will be transcribed and translated, and we will identify any unaddressed themes using a general inductive approach.

Aim 8:

For Aim 8, we will describe the median and ranges of expenses incurred by patients, stratified by whether or not the patient had a surgical site infection. We will also describe the median and range for the normal household expenditures and compare the care expenses relative to normal household expenditures.

Power Analysis:

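### The only cost survey described for Aim 8 is given at discharge, so the costs of any later SSI return visit, readmission or household loss are left out of the comparison by SSI status

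*Combined protocol and SAP*

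**What the plan says.** All references are to the combined protocol and SAP.

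- **Objective.** Specific Aims, Aim 8, undertakes to "assess the direct and indirect costs incurred by the mother and her family, stratified by whether or not she has a surgical site infection".
- **Data collection.** Biostatistical and Qualitative Analysis, Phase 2, gives one source: "For a subset of 50 patients, we will administer at discharge a Financial Risk Protection Survey". Its stated purpose is "to understand the total costs of care and the costs relative to normal household expenditures".
- **Analysis.** The Aim 8 entry under Analysis and Outcomes states: "we will describe the median and ranges of expenses incurred by patients, stratified by whether or not the patient had a surgical site infection".
- **Meaning of discharge.** Elsewhere in Phase 2 the word refers to the end of the cesarean admission. Subject Selection and Enrollment says "Randomization into the three study arms will take place at time of discharge", and Study Procedures has the demographic data collected "via a survey administered by the study data collector at time of discharge".
- **Timing of SSI.** Background says that SSIs in these settings often appear after discharge. Study Procedures says "symptoms for SSI usually develop during the first 6-9 post-operative days". Table 1 in Power Analysis counts SSI returns on days 7-14.
- **Other contacts.** At a return visit, staff take clinical items from the chart. The home interviews on days 22-30 cover reasons for not returning (referred patients in Arms 1 and 2) and follow-up practices (a random sample of Arm 3). Costs are not mentioned in either.

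**The concern.** A cost that has not yet been incurred cannot be recorded at discharge, whatever the survey asks. For an SSI that brings the mother back, the transport, treatment, any readmission and the family's lost income all fall after the survey. Phase 2 gives no voucher or other financial support for returning, so the household bears the cost of travel.

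The SSI and non-SSI groups can still be formed later from the chart and the tracker log, so the planned table can be filled in. It would compare first-stay expenses, while the aim and the survey's stated purpose describe total costs. A reader of the results could take a small difference between the groups as evidence that SSI costs families little, when the relevant costs were never collected.

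**Working it through.** **1. Reproduce the plan's own figures (Power Analysis, Table 1).**
- SSI cases per arm: 364 x 0.15 = 54.6, rounded to 55.
- SSI returns: 55 x 0.80 = 44 in each of Arms 1 and 2; 55 x 0.40 = 22 in Arm 3.
- As a share of the arm: 44/364 = 0.121 and 22/364 = 0.060, the table's 0.12 and 0.06.
- Power for 0.12 against 0.06 with 364 per arm, two-sided alpha 0.05: 0.809, which matches the stated 81%.

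The rates used below are therefore the plan's own, and they are consistent with each other.

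**2. Expected SSI cases among the 50.** Formula: 50 x SSI rate. This assumes that the 50 are not chosen by SSI status; the plan does not say how they are chosen.
- 15% (planning rate): 50 x 0.15 = 7.5, binomial 95% range 3 to 13.
- 10% and 20% (the range in Subject Selection and Enrollment): 5 and 10.

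**3. Expected SSI cases with a return visit after the survey.** Formula: 50 x SSI rate x return rate among SSI cases. The arm make-up of the 50 is not stated, so three cases are shown. The even-mix return rate is (44 + 44 + 22)/165 = 110/165 = 66.7%.

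| Arms of the 50 | Return rate | SSI 10% | SSI 15% | SSI 20% |
|---|---|---|---|---|
| All Arm 3, or Arm 3 rate throughout | 40% | 2.0 | 3.0 | 4.0 |
| Even mix | 66.7% | 3.3 | 5.0 | 6.7 |
| All Arms 1 and 2 | 80% | 4.0 | 6.0 | 8.0 |

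At 15% SSI, the binomial 95% ranges for the three rows are 0 to 7 (probability 0.06), 1 to 9 (0.10) and 2 to 11 (0.12).

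**4. Does the day of discharge matter?** The plan gives no usual day. It excludes patients still in hospital 10 days after surgery, so a few discharges could fall on days 7-9, within Table 1's window and after the usual onset. The result in step 3 does not depend on this, because a return visit follows the discharge at which the survey is given.

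**5. What the counts do not show.** They are return visits, not money. SSI patients who do not return, and mothers without SSI, can also have expenses after discharge that the survey misses.

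**The case against.** The strongest reply has four parts.

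*The reading of discharge is inferred.* Aim 8 does not say which discharge is meant, and the survey (Appendix D) is not in the supplied text, so any instructions in it on timing cannot be checked. This stands as a limit on confidence. However, the use of the word elsewhere in Phase 2 points to the index admission. A survey at discharge from a readmission would in any case miss outpatient returns and later household costs.

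*Some SSI costs may be captured.* Because the day of discharge is not given, an SSI may already be present at the survey. This also stands. A reader might infer that every survey comes before the day 7-14 window, or that no SSI cost at all is recorded. The documents support neither. They support only that the survey comes before any return visit.

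*SSI status can be linked afterwards.* This is correct. A reader might infer that the stratification cannot be done because SSI is often unknown at discharge. That does not follow, since the chart and tracker log supply it later. The gap is in the costs.

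*Aim 8 is small and descriptive.* This is true, and it limits the weight of the point. The mismatch between the stated outcome and the data collected remains.

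**Conclusion.** The concern holds in this form: as written, the plan collects first-stay costs for 50 patients and would report them as the cost of care by SSI status. Return-visit, readmission and later household costs are absent, so the cost of SSI to the household would tend to be understated. The documents contain no cost figures, so the size of that bias in money cannot be estimated.

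At the 15% planning rate, about 7.5 SSI cases are expected among the 50, with about 3 to 6 of them having an uncosted return visit (5 with an even arm mix). Over SSI rates of 10% to 20% the range is 2 to 8. These figures rest on three assumptions: the 50 are not selected by SSI status, the return rates in Table 1 apply, and discharge means the index discharge.

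A reader might infer a threat to the main comparison. There is none: Aim 4 and its power do not use the cost data. The point should be addressed, but it concerns a secondary aim. Confidence is moderate to high, held back by the inferred meaning of discharge and the unseen appendix.

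**What to change.** **Preferred change.** In Biostatistical and Qualitative Analysis, Phase 2, keep the discharge survey for first-stay costs. Add one later contact with the same 50 patients, by phone or visit, made by the existing data collectors in a common window such as the days 22-30 already in use. It should ask about care-related costs and lost income since discharge. Residence is already recorded at baseline for all arms, so only a detailed address or phone number needs adding for the Arm 3 patients in the subset (about 50/3 = 17 if the 50 are spread evenly).

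Under Analysis and Outcomes, Aim 8, report first-stay, post-discharge and total costs by SSI status, with the number not reached. State how the 50 are chosen.

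**Minimum change.** If no later contact is made, restate the Aim 8 outcome as first-stay costs only, and do not present it as the cost of SSI. This needs only a change of wording.

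**Cost of the preferred change.**
- Up to 50 added contacts, 50/1092 = 4.6% of Phase 2 patients.
- Some patients will not be reached, recall will be imperfect, and costs after about day 30 are still missed.
- The consent wording may need to cover the contact.
- Patients would know of a later contact, which could slightly affect return behavior. The plan avoids retention measures for this reason, and its risk section notes that expecting a visit may delay return. Describing the contact neutrally as a cost survey limits this.
- The SSI group stays at about 7 or 8, enough for description only.
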